11 INVESTIGATOR OBLIGATIONS

The Investigator agrees to conduct the clinical study in compliance with this protocol which was approved by the IEC/IRB in compliance with local regulatory requirements. The Investigator and the Sponsor will sign the protocol to confirm this agreement.

11.1 Essential Study Documents

The Investigator is responsible for providing and maintaining essential study documents. Essential study documents are those documents that individually and collectively permit the evaluation of the conduct of the study and the quality of the data produced. These documents serve to demonstrate the compliance of the Investigator and the Sponsor (or an authorized representative) with the standards of GCPs and with all applicable national regulatory requirements.

Essential study documents will include regulatory documents as well as source documents which are original documents, data and records of clinical findings, observations and other activities in a clinical study necessary for the reconstruction and evaluation of the study. Source documents will include hospital records, clinical and office charts, laboratory notes, memoranda, subject diaries or evaluation checklists, pharmacy dispensing records, recorded data from automated instruments, copies or transcriptions certified after verification as being accurate copies, microfiches, photographic negatives, microfilm or magnetic media, x-rays, subject files and records kept at the pharmacy, at the laboratories and at medical/technical departments involved in the clinical study.

The Investigator agrees to allow direct access to all essential clinical study documents for the purpose of monitoring and/or auditing by the Sponsor (or an authorized representative) and inspection by the appropriate national and foreign regulatory authorities.

11.2 Case Report Form (CRF) Completion

Data reflecting the subject's participation with the study drug under investigation will be reported to the Sponsor (or an authorized representative). The data will be recorded on the designated (e)CRFs provided or approved by the Sponsor.

The (e)CRF is essentially considered a data entry form and should not constitute the original (or source) medical records unless otherwise specified. Source documents are all documents used by the Investigator or hospital that relate to the subject's medical history, that verify the existence of the subject, the inclusion and exclusion criteria and all records covering the subject's participation in the study. They include laboratory notes, ECG results, memoranda, pharmacy dispensing records, patient files, etc.

The Investigator is responsible for maintaining source documents. These will be made available for inspection by the study monitor at each monitoring visit. The Investigator must submit a

completed (e)CRF for each subject who did not fail screening. All supportive documentation submitted with the (e)CRF, such as laboratory or hospital records, should be clearly identified with the study and subject number. Any personal information, including subject name, should be removed or rendered illegible to preserve individual confidentiality.

All data must be entered in English. The (e)CRFs should always reflect the latest observations on the subjects participating in the trial. Therefore, the (e)CRFs are to be completed as soon as possible after the subject's eligibility has been confirmed and thereafter during or after the subject's visit. To avoid inter observer variability, every effort should be made to ensure that the same individual who made the initial baseline determinations completes all efficacy and safety evaluations. The Investigator must verify that all data entries in the (e)CRFs are accurate and correct. If some assessments are not done, or if certain information is not available or not applicable or unknown, the Investigator should indicate this in the (e)CRF. The Investigator will be required to (electronically) sign off on the clinical data.

The monitor will review the (e)CRFs and evaluate them for completeness and consistency. The (e)CRF will be compared with the source documents to ensure that there are no discrepancies between critical data. All entries, corrections and alterations are to be made by the responsible Investigator or his/her designee. The monitor is not allowed to enter data in the (e)CRFs.

If additional corrections are needed, the responsible monitor or Data Manager will raise a query. The appropriate investigational staff will answer queries sent to the Investigator.

In case screen failure data is entered in the (e)CRF, these data should be clearly indicated in the raw datasets and removed from the analysis datasets.

11.3 Essential Records Retention

The Investigator should maintain the essential clinical study documents (including CRFs, source documents, clinical drug disposition records, signed subject informed consent forms, AE reports and other regulatory documents) as required by the applicable national regulatory requirements. The Investigator is to take adequate measures to prevent accidental or premature destruction of these documents. In the event of accidental destruction, the Investigator should notify the Sponsor (or an authorized representative) immediately.

Essential clinical study documents will be retained at least two (2) years after the last approval of a marketing application in an ICH region and until there are no pending or contemplated marketing applications in an ICH region OR at least two (2) years have elapsed since the formal discontinuation of clinical development of the investigational product. These documents shall be retained for a longer period, however, if required by the applicable regulatory requirements or by an agreement with the Sponsor (or an authorized representative).

The Investigator is required to notify the Sponsor (or an authorized representative) prior to changing the location or status of any essential clinical study documents. The Sponsor (or an authorized representative) will be responsible for informing the Investigator as to when these documents no longer need to be retained.

11.4 Investigator Agreement

The Investigator is responsible for assuring the proper implementation and conduct of the clinical study including those study-related duties delegated to other appropriately qualified individuals. The Investigator and his/her staff will cooperate with the Sponsor (or an authorized representative) during monitoring and auditing visits to assist with the review of the study data and resolve any discrepancies.

The Investigator will demonstrate due diligence in recruitment and screening of potential study subjects. The enrollment rate should be sufficient to complete the study as agreed with the Sponsor (or an authorized representative). The Sponsor (or an authorized representative) is to be notified of any projected delays, which may impact the completion of the study.

The Sponsor retains the right to terminate the clinical study at any time for any reason. In such an event, instructions on the requirements for the discontinuation of subjects will be provided by the Sponsor (or an authorized representative).

12 SPONSOR OBLIGATIONS

12.1 Protocol Amendments

Only the Sponsor (or an authorized representative) will make modifications to the clinical study protocol, which will be documented in a written amendment that describes all changes that will be implemented. Protocol amendments will be categorized as either substantial or non-substantial.

Protocol amendments will be considered substantial when the changes have significant impact on:

- The safety of physical or mental integrity of the subjects
- The scientific value of the study
- The conduct or management of the study
- The quality or safety of any investigational medicinal product or control used in the study

Protocol amendments will be considered non-substantial when the changes affect only administrative issues with the conduct of the study, i.e., changes in telephone numbers or addresses.

The Sponsor (or an authorized representative) will be responsible for notifying the appropriate national regulatory authorities in writing of any amendments to the protocol prior to the changes being implemented except in those cases where the changes are necessary to eliminate an immediate hazard to the clinical study subjects.

Substantial amendments will require written approval by the IEC/IRB prior to being implemented by the Investigator at the study site except under those circumstances described previously. Non-substantial amendments will not require approval by the IEC/IRB unless requested by the IEC/IRB.

12.2 Study Monitoring

The study will be monitored by authorized representatives of the Sponsor throughout its duration by means of personal visits to the Investigator's facilities and through other communications (e.g., telephone calls, written correspondence). Monitoring visits will be scheduled at mutually agreeable times periodically throughout the study and at frequency deemed appropriate for the study.

These visits will be conducted to evaluate the progress of the study, ensure the rights and well-being of the subjects are protected, check that the reported clinical study data are accurate, complete and verifiable from source documents, and the conduct of the study is in compliance with the approved protocol and amendments, GCPs and applicable national regulatory requirements. A monitoring visit will include a review of the essential clinical study documents

(regulatory documents, CRFs, source documents, drug disposition records, subject informed consent forms, etc.) as well as discussion on the conduct of the study with the Investigator and staff. The Investigator and staff should be available during these visits to facilitate the review of the clinical study records and resolve/document any discrepancies found during the visit.

12.3 Quality Assurance Audits

The Sponsor's (or an authorized representative's) Quality Assurance department may conduct on-site audits of all aspects of the clinical study either during the study or after the study has been completed.

The clinical study may also be subject to inspection by regulatory authorities (national or foreign) as well as the IECs/IRBs to ascertain that the study is being or has been conducted in accordance with protocol requirements, GCPs, as well as the applicable regulatory requirements.

13 PUBLICATION POLICY

The data generated by this study are confidential information of the Sponsor. The Sponsor will publicly disclose the results of all applicable clinical trials following legal and regulatory requirements. The publication policy with respect to the Investigator and study center will be set forth in the Clinical Trial Agreement.

14 **INSURANCE**

The Sponsor has taken out a liability insurance, which covers this study as required by local law and/or national regulations and/or ICH guidelines whichever is applicable.

1. INTRODUCTION

This statistical analysis plan (SAP) is based on protocol RACE3002 Version Date 09 OCT 2017, Amendment 1 Date 07 NOV 2018, Amendment 2 Date 22 NOV 2019, TFDA Official Letter (No. 1096009485) dated 08-Jun-2020 as well as Abbott Clarification Letter for Interim Analysis dated 20-Aug-2020. The SAP provides details of data handling procedures, statistical analysis methods for efficacy and safety evaluations. It also outlines statistical programming specifications for tables and listings, and other details on the analyses not provided in the study protocol.

All data of these enrolled and randomized subjects using Protocol Version Date 09 OCT 2017 will be listed only. A note to file (NTF), Racecadotril dosage per sachet dated on 21-Mar-2019 is adapted for Racecadotril dosage collection.

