4.2 Categorical Endpoints

For qualitative variables, per category the numbers and frequencies of subjects with non-missing data (n, %) will be the default summary presentation, and if appropriate and present, the number of missing values. Percentages will be presented with 2 decimals. Partial date(s) will be listed as provided in the listings.

For AEs, medical history and concomitant medications, however, the denominator for the percentage calculation will be the number of subjects at risk. A subject will be considered at risk if the subject is in the safety sample and entered the respective study period.

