6. ANALYSIS OF SUBJECT SAMPLES

The main subject samples of interest are defined as follows.

The all subjects consented sample will consist of all subjects who:

- Gave their informed consent.

The all subjects <allocated to treatment> sample will consist of all subjects who:

- Were in the all subjects consented sample; and
- Were <allocated to treatment>

The safety sample will consist of all subjects who:

- Were in the all subjects allocated to treatment sample; and
- Had at least one dose of study medication administered.

The full analysis (FA) sample will consist of all subjects who:

- Were included in the safety sample; and

- Had data for at least one post-baseline assessment of any efficacy measurement.

The per-protocol (PP) sample will be defined through blind data review and will consist of all subjects who:

- Were included in the FA sample; and
- Did not present any major protocol violation.

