9.2.5 Number of Stools and Watery Stools (Additional Table Requested by Abbott)

Number of stools as well as number of watery stools from start of treatment and until end of study treatment and for each day of the study will be summarized as Table 14.2.5 using FA and PP samples.

Subgroup analysis of number of stools as well as number of watery stools by age group (< 24 months old and \geq 24 months old) will be also summarized as Table 14.2.10 using FA and PP samples.

10.EXTENT OF EXPOSURE AND DRUG COMPLIANCE

The randomization (only for Protocol Version dated 09 OCT 2017) will be listed in Listing 16.2.5.1.

All study drug dispensation and retrieve to each subject will be listed in Listing 16.2.5.2. Individual subject study drug administration record will be listed in Listing 16.2.5.2. In listing 16.2.5.2, for data collection of Racecadotril dosage, a NTF (Abbott_RACE3002_NTF_Racecadotril dosage per sachet_20190321) from Abbott is adapted to extract the dosage with unit from column of "Relevant Information Related to Study Drug Dispensation".

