10.2 Drug Compliance

The way of computing the drug compliance is listed as below,

The study drug compliance = Number of sachets a subject takes during the treatment period / Number of sachets scheduled to be taken during that treatment period)*100%

The drug compliance for the treatment group will be summarized as Table 14.1.3 using Safety, FA and PP samples as well.

11.SAFETY ANALYSIS

The safety sample will be used for the analysis of the safety and tolerability data.

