11.1 Adverse Events

AEs are considered treatment emergent (TE) if they start or worsen at or after the first administration of study drug and before or on the day of last administration of study drug plus a gap period of 1 day.

AEs will be reported on a per-subject basis, i.e. counting subjects rather than events. This means that if a subject suffers the same AEs repeatedly during the applicable study period, the event will be counted only once for that period. Repeated events per subject will be summarized according to the following rule: if a subject suffered the same AE more than once, the event will be assigned the

worst severity, the closest relationship to the study drug and the earliest starting date. Only treatment emergent AEs will be reported. In the listings, however, all occurrences of the AEs will be presented.

Treatment emergent AEs will be summarized per primary SOC, per HLT by primary SOC and per PT by HLT and primary SOC. Severity and drug-event relationship of treatment emergent AEs are summarized separately. Non-TEAEs will be listed.

All adverse event data will be listed in Listing 16.2.7. A general summary of all AEs, TEAEs and SAEs will be provided in Table 14.3.1.1.

Other summary tables for adverse events will be summarized:

- Table 14.3.1.2: Incidence of Treatment-Emergent Adverse Events MedDRA
- Table 14.3.1.3: Incidence of Treatment-Emergent Adverse Events >= 5% of the Subjects in the Treatment Group
- Table 14.3.1.4: Incidence of Treatment Emergent Adverse Events by Reasonable Possibility for a Causal Relationship MedDRA
- Table 14.3.1.5: Incidence of Treatment Emergent Adverse Events by Severity MedDRA

Subgroup analysis of number of stools per day as well as number of watery stools by age group (< 24 months old and \geq 24 months old) will be also summarized:

- Table 14.3.1.6: Subgroup of Treatment-Emergent Adverse Events
- Table 14.3.1.7: Subgroup of Incidence of Treatment-Emergent Adverse Events MedDRA
- Table 14.3.1.8: Subgroup of Incidence of Treatment-Emergent Adverse Events >= 5% of the Subjects in the Treatment Group
- Table 14.3.1.9: Subgroup of Incidence of Treatment Emergent Adverse Events by Reasonable Possibility for a Causal Relationship - MedDRA
- Table 14.3.1.10: Subgroup of Incidence of Treatment Emergent Adverse Events by Severity MedDRA

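### Any child dosed with Racecadotril under the 2017 protocol version meets the SAP's safety-sample definition, yet would be left out of the adverse-event tables

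*SAP*

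**What the plan says.** The rule on the earlier cohort stands in SAP section 1: "All data of these enrolled and randomized subjects using Protocol Version Date 09 OCT 2017 will be listed only". Two other places treat these children as a separate group. SAP section 3.9 leaves them out of the dry run of tables, and the opening of SAP section 10 gives them their own listing: "The randomization (only for Protocol Version dated 09 OCT 2017) will be listed in Listing 16.2.5.1".

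SAP section 6 builds the safety sample from two conditions: "Were in the all subjects allocated to treatment sample; and" and "Had at least one dose of study medication administered". Protocol section 10.2 has the same two conditions. Neither place mentions the protocol version.

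The opening of SAP section 11 then says: "The safety sample will be used for the analysis of the safety and tolerability data". SAP section 4.2 ties the denominator for AE percentages to the same sample: "A subject will be considered at risk if the subject is in the safety sample and entered the respective study period". For output, SAP section 11.1 promises: "A general summary of all AEs, TEAEs and SAEs will be provided in Table 14.3.1.1", and separately: "All adverse event data will be listed in Listing 16.2.7".

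**The concern.** One rule puts a dosed child from the 2017 version into the safety tables and the other takes the same child out. If section 1 is followed, the AE tables are not built on the safety sample that the SAP and the protocol define. The overview table would not cover all AEs, TEAEs and SAEs, although it is described that way.

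The safety objective (Protocol 3.3, SAP 2.3) is to evaluate safety and tolerability of Racecadotril with oral rehydration solution. With at most 48 children enrolled, each exposed child carries weight in an incidence table. A reader who relies on the tables would not see that some exposed children are absent from both the count and the denominator.

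**Working it through.** The check is mainly a comparison of the text.

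1. **Do these children form a real group?** Yes. SAP sections 1, 3.9 and 10 each give a rule for subjects under the 09 OCT 2017 version, and section 10 plans a randomization listing for that version alone. They were therefore assigned to treatment, which bears on the first safety-sample condition.
2. **Do they meet the second condition?** Those who took at least one dose of study medication do. The documents do not describe the 2017 arms. A child randomized to an arm without study medication would not meet it. The point is therefore limited to children dosed with Racecadotril.
3. **Does any text exclude them from the sample?** No. SAP section 6 and Protocol section 10.2 contain no criterion on version. SAP section 7 requires a reason in Listing 16.2.3 for each subject left out of the safety sample, but section 6 supplies no ground that could be entered there for these children.
4. **Is the rule marked as a departure from the protocol?** No. SAP section 3.10 says openly that its weight-group analysis is not in the protocol. Section 1 makes no such remark about Protocol section 10.2 and gives no reason.
5. **Where would their events appear?** In Listing 16.2.7, which takes all AE data. They would not appear in Tables 14.3.1.1 to 14.3.1.5.
6. **Do they count toward recruitment?** Neither document says whether they count toward the maximum of 48 enrolled or the 40 completers (Protocol 10.8; SAP 3.4 and 4.4).

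**Size.** The plan gives no figure on this point. Its one precision figure, 3.1 percentage points, concerns recovery and is not used here. Let k be the number of children dosed with Racecadotril under the 2017 version, and n the number in the AE tables. The share of dosed children left out is k / (n + k). The values of k are assumptions. For n, 40 is the completer target and 48 the enrolment maximum; dosed drop-outs stay in the safety sample, so n can exceed 40.

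| k (assumed) | n = 40 | n = 48 |
|---|---|---|
| 0 | 0% | 0% |
| 1 | 1/41 = 2.4% | 1/49 = 2.0% |
| 5 | 5/45 = 11.1% | 5/53 = 9.4% |
| 10 | 10/50 = 20.0% | 10/58 = 17.2% |
| 20 | 20/60 = 33.3% | 20/68 = 29.4% |

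This treats the 2017-version children as additional to the 48. If they count within the 48, then at full enrolment n = 48 − k and the share is k/48, for example 10/48 = 20.8%.

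**The case against.** The strongest reply is that section 1 is a specific scope rule and section 6 a general definition carried over from the protocol. Sections 3.9 and 10 handle the 2017-version children in the same separate way, so a programmer would know to leave them out, and all that is missing is a cross-reference. It stands that the output is predictable. But a predictable omission still leaves the safety tables at odds with the definition in both documents, and no reason is given.

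It also stands that leaving these children out of efficacy may well be sound, since randomization applied to the 2017 version only and the current design is single-arm. The amendments and letters cited in section 1 may contain a reason that covers safety too. If so, the SAP should state it.

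A reader might infer more than the documents support:

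- *That the children were dropped after their open-label results were known.* The open-label statements (Protocol 7.6, SAP 3.3) describe the current design, not the 2017 one. The date on which the rule was adopted is not visible, so data-driven exclusion cannot be inferred.
- *That adverse events are being hidden.* All AE data go into Listing 16.2.7, and Protocol section 1.1 requires SAEs to be reported to ethics committees and authorities.
- *That the tables would understate the SAE rate by a given amount.* That needs a number of dosed children and a number of events, and the documents give neither.

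**Conclusion.** The inconsistency holds and should be corrected. Under SAP section 1, any child dosed with Racecadotril under the 2017 version is absent from the AE tables and their denominators. Under SAP section 6 and Protocol section 10.2, the same child is in the safety sample on which those tables rest.

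The conclusion is conditional on at least one such child having been dosed, which the documents neither confirm nor exclude. The size is unknown; the shares in the table above only show how it depends on the count. The loss concerns tabulation, not disclosure, and the point does not extend to the exclusion from efficacy, which the design change may justify.

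**What to change.** - **SAP section 6:** state that the FA and PP samples cover only subjects enrolled under the amended versions, and give the reason. Keep the safety sample as defined, and limit the sentence in section 1 to match.
- **Table 14.1.1:** report how many subjects were enrolled and how many were dosed under the 2017 version, and say whether they count toward the 48 and the 40.
- **Tables 14.3.1.1 to 14.3.1.5:** show all Racecadotril-dosed children in three columns: amended version, 2017 version and total.
- **Other tables on the safety sample** (exposure, vital signs, AE tables by age group): state whether they include the 2017-version children.

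The cost is two columns beyond the present one, filled from data already planned for the listings. The downside is a total that mixes two designs, which the separate columns show openly. Writing a version restriction and its reason into the safety-sample definition would also remove the contradiction within the SAP. It would, however, depart from Protocol section 10.2 and still leave exposed children out of the tables, so it is the weaker repair.
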